5.1.3.4. EuroQOL-5 Dimension-5 Level

The EuroQol 5-dimension, 5 severity level (EQ-5D-5L) questionnaire is a brief, validated, HR-QOL instrument that is intended to assess the patient's health status at the time of administration. The questionnaire contains 5 dimensions (mobility, self-care, usual activities, pain/discomfort, and anxiety/depression), each of which includes 5 response variables (no problems, slight problems, moderate problems, severe problems, and extreme problems). A 5-digit profile based on each of the dimensions can be further converted to a single numerical score called an index. Value sets (a collection of index values) have been derived for multiple countries/regions. Higher index scores indicate better quality of life.

A vertical visual analogue scale (VAS) is included for the patients to indicate a self-rated estimate of their health. The VAS ranges from 100 (best health you can imagine) to 0 (worst health you can imagine).

The EQ-5D-5L questionnaire and VAS are anticipated to be completed in several minutes and can be completed by the patient, via an interviewer (in-person or over the telephone); or via proxy.

5.2. Safety

The safety of ravulizumab will be assessed based on adverse events (AEs), serious adverse events (SAEs), and changes from baseline through study completion in vital signs, routine clinical laboratory tests (eg, chemistry, hematology), physical examination, electrocardiogram results, and pregnancy tests for female patients.

5.2.1. Adverse Events (AEs)

Adverse events are defined in Protocol Section 10.3.

All AEs and SAEs will be collected from the signing of the informed consent form (ICF) until the last visit at the time points specified in the Schedule of Activities (SoA) (see Protocol Section 1.3).

For the purposes of this SAP, 4 types of AEs will be noted:

- Pre-treatment adverse events and serious adverse events (PTAEs and PTSAEs)
- Treatment-emergent adverse events (TEAEs)
- Treatment-emergent serious adverse events (TESAEs)

The PTAEs/PTSAs are the AEs/SAEs that occur between the signing of informed consent and Day 1. The TEAEs/TESAEs are AEs/SAEs with onset on or after Day 1.

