#### **8.4.11. Follow-up Monitoring**

Follow-up visits will be conducted as indicated in the SoA ([Table 1](#)) to review patient status; including survival, monitoring for pregnancy, and to obtain information about new or worsening treatment-emergent SAEs (TESAEs). The follow-up visits will be conducted as a telephone call if the patient is discharged from the hospital or an in person visit if the patient is still hospitalized.

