Follow-up of AEs and SAEs

• The Investigator is obligated to perform or arrange for the conduct of supplemental measurements and/or evaluations as medically indicated or as requested by Alexion to elucidate the nature and/or causality of the AE or SAE as fully as possible. This may include additional laboratory tests or investigations, histopathological examinations, or consultation with other health care professionals.

• New or updated information will be recorded in the originally completed CRF/eCRF.

• The Investigator will submit any updated SAE data to Alexion within 24 hours of receipt of the information.

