7.3.2. Adverse Events (AEs)

The AEs will be coded by primary System Organ Class (SOC) and Preferred Term (PT) using MedDRA (version 23.0 or higher).

For the purposes of this SAP, only Treatment-Emergent Adverse Events (TEAEs) will be summarized. TEAEs are AEs that onset on or after Day 1 in the study. Both tabular outputs and listings will be created for TEAEs as described in this SAP; additional details regarding AEs are outlined in [Appendix 9.4.7](#).

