9.4.7. Adverse Events

The analysis of AEs is described in [Section 7.3.2](#).

Treatment-emergent AEs are events with onset dates on or after Day 1 in the study. If the start date of an AE is partially or completely missing and the end (stop) date and time of the AE does not indicate that it occurred prior to Day 1, then the determination of treatment-emergent status will be based on the following:

- If the start year is after the year of Day 1, then the AE is treatment-emergent; else,
- If the start year is the same as the year of Day 1 and
 - the start month is missing, then the AE is treatment emergent; else if

- the start month is present and is the same or after the month of Day 1, then the AE is treatment-emergent; else,
- If the start date is completely missing, then the AE is treatment-emergent.

All other AEs are considered PTAEs.

Patient percentages will be based on the total number of patients in the particular treatment group.

AEs with missing relationship will be assumed to be related to study treatment. AEs with missing toxicity grade will be summarized as a separate category.

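### Treatment emergence is decided by onset date alone, so a screening-period AE that worsens after Day 1 but stays on its original record is missing from the by-arm TEAE and TESAE tables

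*SAP*

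**What the plan says.** The SAP gives the rule three times, always by onset.

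- SAP 5.2.1: "The TEAEs/TESAEs are AEs/SAEs with onset on or after Day 1". Pre-treatment events are the "AEs/SAEs that occur between the signing of informed consent and Day 1".
- SAP 7.3.2: "only Treatment-Emergent Adverse Events (TEAEs) will be summarized. TEAEs are AEs that onset on or after Day 1 in the study".
- SAP 9.4.7: "Treatment-emergent AEs are events with onset dates on or after Day 1 in the study". After the partial-date rules it closes the set: "All other AEs are considered PTAEs".

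Protocol 9.4.2 is onset-only too, although it anchors onset to treatment with ravulizumab and not to Day 1.

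On recording, Protocol 10.3.3 says, under follow-up of AEs and SAEs: "New or updated information will be recorded in the originally completed CRF/eCRF". Protocol 10.3.1, which SAP 5.2.1 adopts as the AE definition, counts an exacerbation of a chronic or intermittent pre-existing condition as an AE. It leaves out fluctuations of conditions present at study start only when they do not worsen.

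Pre-treatment AEs do go into the detailed listings, which carry seriousness, toxicity grade and outcome (SAP 7.3.2.2). Patients who die have their own summary table and listing (SAP 7.2.1).

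**The concern.** The incidence of TEAEs and TESAEs is the only safety endpoint listed in Protocol Section 3, and Protocol Table 2 names serious infection as a potential risk of C5 inhibition. AEs are collected from consent, so an infection can begin during screening, be recorded as a non-serious AE, and become serious or fatal after Day 1. Under the SAP rule its start date fixes it as pre-treatment, whatever follows.

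Two things are at stake. The by-arm tables can omit an event whose important part happened on treatment. And because neither document says whether the worsening of an already recorded AE gets a new record, its class may depend on how a site fills in the form. The study is open-label (Protocol 6.3), so that choice is made with the treatment arm known and need not balance out.

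**Working it through.** The documents give no figure for this point, so there is none to reproduce. The check is to apply the SAP 9.4.7 rule to test cases and then set the recording texts side by side.

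**Rule.** With a complete start date, an AE is a TEAE if the start date is on or after Day 1, and otherwise a PTAE. With a missing start day, the same year as Day 1, a start month equal to or later than that of Day 1, and no end date before Day 1, it is a TEAE.

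**Cases**, with Day 1 set to 15 June 2020 for illustration:

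| Case | Start date on record | Class |
|---|---|---|
| a. Starts 13 June, grade rises 17 June, same record | 13 June | PTAE |
| b. Starts 13 June, becomes serious 18 June, same record | 13 June | PTAE |
| c. Starts 14 June, fatal 25 June, same record | 14 June | PTAE |
| d. Worsening on 17 June entered as a new AE | 17 June | TEAE |
| e. Starts 15 June, before the infusion that day | 15 June | TEAE |
| f. True start 13 June, day missing on the form | June | TEAE |

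Cases a to c are the gap. Because "only Treatment-Emergent Adverse Events (TEAEs) will be summarized", these events are absent from the overall summary, the SOC and PT tables, the toxicity-grade table and the summary of TEAEs leading to death (SAP 7.3.2.1, 7.3.2.2 and 7.3.2.4). Cases a and b appear only in listings; case c also appears in the death summary.

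Cases d to f bound the gap. Case d is the same clinical course as case a, recorded differently, and it changes class. Case e shows that an event arising on Day 1 itself already counts. Case f counts only because data are incomplete.

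**Which record is used?** Protocol 10.3.3 points to the original record, which gives a to c. Protocol 10.3.1 makes an exacerbation an AE in its own right, which gives d. But 10.3.1 speaks of chronic or intermittent pre-existing conditions, and an acute event that arises during screening does not clearly fit. Neither text states a rule for it.

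**Length of the window.** Screening lasts up to 3 days (Protocol 4.1) and may fall on the same day as Day 1 (Protocol 1.3, footnote 1). The exposed interval is therefore 0 to 3 days.

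**The case against.** The strongest reply is that the protocol's AE definition already brings worsening into the tables. An exacerbation can be an AE with its own onset after Day 1, and hence a TEAE. The sentence in Protocol 10.3.3 sits among instructions on follow-up measurements; it says nothing of onset dates and does not forbid a new record. CRF completion guidance might settle the matter, and it is not among the documents. This stands to the extent that the omission depends on the worsening staying on the original record. It does not remove the gap, because the plan leaves that to site practice.

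It is also fair that the SAP does not depart from the protocol here, since Protocol 9.4.2 is onset-only as well, and that the SAP applies its Day 1 rule in both arms.

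Three stronger readings are tempting and are not supported.

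- A reader might infer that every such event drops out of every TEAE and TESAE table. Cases d and f show otherwise, and deaths are summarized separately.
- A reader might infer that worsening of any infection already present when dosing starts is lost. Infections present before consent are not PTAEs, because AE collection starts at consent. Only events that first arise between consent and Day 1 are exposed.
- A reader might see a conflict with Protocol 8.4.11, where follow-up is "to obtain information about new or worsening treatment-emergent SAEs (TESAEs"). That text concerns events that are already treatment-emergent, so it does not contradict the SAP.

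**Conclusion.** The point holds in a limited form. As written, the rule leaves out of the by-arm TEAE and TESAE tables any AE that first arises between consent and Day 1, is kept on its original record, and then rises in grade, becomes serious or is fatal on or after Day 1. Whether a given event meets that condition depends on recording practice that the documents do not fix.

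The number affected is probably small, because the window is 0 to 3 days, and it cannot be quantified. A reader might supply rates. For instance, if 5% to 20% of patients had a pre-Day 1 AE and 20% to 40% of those worsened, the count would run from 180 × 0.05 × 0.20 = 1.8 to 180 × 0.20 × 0.40 = 14.4 patients on ravulizumab, and from 90 × 0.05 × 0.20 = 0.9 to 90 × 0.20 × 0.40 = 7.2 on BSC. The documents give neither share, and the upper ends allow neither for a short or zero window nor for worsenings that receive their own record. These figures should not be read as an estimate.

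The change is still worth making: it concerns the only listed safety endpoint, the gap comes from a stated rule and not from a missing detail, and the remedy is cheap.

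**What to change.** 1. In SAP 5.2.1, 7.3.2 and 9.4.7, define a TEAE or TESAE as an AE or SAE that starts on or after Day 1, or that starts before Day 1 and increases in toxicity grade, becomes serious or becomes fatal on or after Day 1. Apply the definition identically in both arms.
2. Align Protocol 9.4.2 with this, or record the difference in SAP 4.1.
3. State, consistently with Protocol 10.3.3, whether such a worsening is captured on the original record with a date of worsening or on a new dated record. Use one route only, so that it is counted once.

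The cost is a change of wording, one extra derivation that needs the date of worsening, and a CRF guidance note. TEAE and TESAE counts will be slightly higher in both arms.

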5.2.2. Vital Signs

Temperature (°C or °F), heart rate (HR, beats per minute), respiratory rate (breaths per minute), and systolic and diastolic blood pressure (SBP and DBP) (millimeters of mercury [mm Hg]) will be assessed.

Body weight will be measured in kilograms (kg).

5.2.3. Laboratory Assessments

Clinical chemistry, hematology, coagulation, urinalysis, arterial blood gas (partial pressure of oxygen [PaO₂]), pregnancy test, and direct Coombs test will be collected as outlined in the protocol (see Protocol Section 1.3 and Protocol Table 9) and will be analyzed by the local laboratory.

5.2.4. Other Safety Assessments

5.2.4.1. Physical Examination

Complete or abbreviated physical examination is to be performed at the timepoints indicated in the SoA (see Protocol Section 1.3). A complete physical examination will include, at a minimum, assessments of the following organs/body systems: skin, head, ears, eyes, nose, throat, neck, lymph nodes, chest, heart, abdomen, extremities, and musculoskeletal. An abbreviated physical examination consists of at least an evaluation of the respiratory and cardiovascular systems. Clinically significant abnormalities or findings will be recorded as AEs.

5.2.4.2. Electrocardiogram (ECG)

A single 12-lead ECG will be conducted to obtain HR, PR interval, QRS interval, RR interval, QT interval, and QTcF. Whether the ECG is within normal limits and the clinical significance of abnormal results will be documented.

5.3. Pharmacokinetic/Pharmacodynamic/Immunogenicity

Samples will be collected as specified in the SoA (see Protocol Section 1.3) to determine serum concentrations of ravulizumab and total and free C5. The actual date and time (24-hour clock time) of each sample will be recorded.

Antibodies to ravulizumab (ie, antidrug antibody [ADA]) will be evaluated in serum samples collected from patients according to the SoA (see Protocol Section 1.3). Serum samples will be screened for antibodies binding to ravulizumab. Confirmed antibody positive samples will be further evaluated for antibody titer and the presence of neutralizing antibodies.

5.4. Biomarkers

Blood samples for biomarker analyses will be collected at the timepoints indicated in the SoA (see Protocol Section 1.3) to evaluate complement activation and related pathways and cardiovascular health, and their clinical response to ravulizumab. These biomarkers include complement pathway proteins (eg, total and free C5, soluble C5b-9 [sC5b-9]), cytokines associated with inflammation and disease (eg, interleukin [IL]-1, IL-2R, IL-6, IL-8, IL-21, tumor necrosis factor [TNF]-b, Pentraxin-3, Citrullinated histone H3, and monocyte chemoattractant protein [MCP]-1), Factor II, and markers associated with cardiovascular disease (procalcitonin, myoglobin, high sensitivity troponin I [hs-TnI] and N-terminal pro-b-type natriuretic peptide [NT-proBNP]).

6. DATA SETS ANALYZED (STUDY POPULATIONS)

This study will employ a two-arm parallel treatment design. Analyses of efficacy endpoints will be performed on the Intent-to-Treat (ITT) population as well as the Per Protocol Set (PPS). The safety analyses will be based on the Safety Set (SS). Subgroups may be analyzed, as indicated in this SAP.

6.1. Intent-to-Treat (ITT) Population

The ITT population consists of all randomized patients and participants will be analyzed as randomized. The ITT population will be used for the analysis of efficacy data and is considered the primary analysis population.

6.2. Per Protocol Set (PPS)

The PPS is a subset of the ITT population without any important protocol deviations that could impact efficacy analyses. The PPS will include all patients who:

- Have no important protocol deviations or key inclusion/exclusion criteria deviations that might potentially affect efficacy,
- Are randomized to the ravulizumab + BSC group and receive 100% of the required treatment doses while they were in the treatment period in the ICU.

Important protocol deviation and key inclusion/exclusion criteria that will result in excluding patients from the PPS are discussed in [Section 7.1.2](#).

For ITT patients in the study who either die or are discharged from the ICU prior to Day 29, the compliance calculation for the per protocol set will include only the time period from the day of first dose to the day of death or ICU discharge.

The PPS will be determined prior to database lock and will be used in a sensitivity analysis of the primary and secondary efficacy endpoints.

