### 9.3. Populations for Analyses

The population sets used for analysis sets are defined in the following:

Analysis Set	Description
Intent to Treat (ITT)	The ITT consists of all randomized patients and participants will be analyzed as randomized.  The ITT will be used for the analysis of efficacy data and is considered the primary analysis population.
Per-Protocol Set (PPS)	The PPS is a subset of the ITT without any important protocol deviations that could impact efficacy analyses. Determination of applicable important protocol deviations for this purpose will be made prior to database lock.  The PPS will be used for sensitivity analyses of the primary and secondary efficacy endpoints.
Safety Set (SS)	The SS consists of all randomized patients who receive at least 1 dose of ravulizumab for patients randomized to ravulizumab + BSC or who were randomized to BSC alone. The SS will be used for the analysis of safety data.

Abbreviation: BSC = best supportive care.

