7.1.3. Demographics, Disease Characteristics, and Medical History

Patient demographic and baseline disease characteristics will be summarized by treatment group and randomization stratification factor using the ITT population and the PPS. Summary statistics will be presented. No formal hypothesis testing will be performed. By-patient listings will be produced.

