7.2.1.5. Sensitivity and Supplementary Analyses

Sensitivity and supplementary analyses for the primary endpoint are described in [Section 7.2.1](#). Briefly these analyses include:

- Different missing data mechanisms to assess the impact of missing data
- Time to event analysis
- Categorical analysis
- Logistic regression model
- Cox proportion hazards model
- The primary analyses described for the ITT population will also be performed using the PPS

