7.2.2. Secondary Analyses

A closed testing procedure will be applied to control the type I error for the analyses of the primary and secondary endpoints at Day 29. If the primary endpoint is statistically significant in favor of ravulizumab, the secondary endpoints will be evaluated according to the following rank order:

1. Number of days free of mechanical ventilation at Day 29,
2. Duration of ICU stay at Day 29,
3. Change from baseline in SOFA score at Day 29,
4. Change from baseline in SpO₂/FiO₂ at Day 29,
5. Duration of hospitalization at Day 29.

The hypothesis testing will proceed from highest rank (#1) the number of days free of mechanical ventilation at Day 29 to the lowest rank (#5) duration of hospitalization at Day 29, and if statistical significance is not achieved at an endpoint ($p \geq 0.05$), then endpoints of lower rank will not be considered to be statistically significant. Confidence intervals and p-values will be presented for all secondary efficacy endpoints for descriptive purposes, regardless of the outcome of the closed testing procedure.

An additional secondary endpoint will be assessed beyond Day 29 regardless of the results of the closed testing procedure: Survival (based on all-cause mortality) at Day 60 and Day 90.

The PPS will be used in a sensitivity analysis for all secondary efficacy endpoints.

7.2.2.1. Number of Days Free of Mechanical Ventilation at Day 29

The number of days free of mechanical ventilation at Day 29 will be summarized by treatment group for all patients and by mortality. The number of days free of mechanical ventilation at Day 29 will be compared between treatment groups using an analysis of covariance (ANCOVA), adjusting for age and the randomization stratification factor, among survivors (ie, the number of days alive and free of mechanical ventilation).

Missing data will be imputed using a multiple imputation approach assuming the data are MAR and using a regression model with covariates for treatment group, the randomization stratification factor, age, sex and presence of a pre-existing condition at baseline (diabetes mellitus, obesity, respiratory condition, and/or coronary artery disease). Sensitivity analyses will include:

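### As literally worded, the second inclusion bullet in SAP 6.2 leaves the Per Protocol Set with no control arm; this is a drafting error confined to the PPS sensitivity analyses

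*SAP*

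**What the plan says.** SAP 6.2 opens with a general definition: "The PPS is a subset of the ITT population without any important protocol deviations that could impact efficacy analyses". It then says which patients the set will include, in two bullets:

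- Bullet 1: "Have no important protocol deviations or key inclusion/exclusion criteria deviations that might potentially affect efficacy".
- Bullet 2: "Are randomized to the ravulizumab + BSC group and receive 100% of the required treatment doses", limited to the time in the treatment period in the ICU.

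Nothing joins the bullets with an 'or', nothing makes bullet 2 conditional on arm, and no line covers BSC alone. A later paragraph limits the compliance calculation, for patients who die or leave the ICU before Day 29, to the time from first dose to that event.

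The set has several uses. SAP 6.2 says it "will be used in a sensitivity analysis of the primary and secondary efficacy endpoints", and Protocol 9.3 agrees: "The PPS will be used for sensitivity analyses of the primary and secondary efficacy endpoints". SAP 7.2.1.5 states: "The primary analyses described for the ITT population will also be performed using the PPS". SAP 7.2.2 adds: "The PPS will be used in a sensitivity analysis for all secondary efficacy endpoints". Under SAP 7.1.3, baseline characteristics "will be summarized by treatment group and randomization stratification factor using the ITT population and the PPS".

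SAP 7.1.2 lists the deviations that remove a patient from the PPS. Receiving fewer than all required doses while alive and in the ICU is one of them. It is filed under the key exclusion criteria, with no arm named.

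**The concern.** A list of conditions under a single 'all patients who' is ordinarily read as joint: a patient must meet each one. Bullet 2 contains an arm assignment, so under that reading membership requires randomization to ravulizumab + BSC. The analyses assigned to the PPS are comparisons between arms, and a one-arm set cannot supply them.

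What is at stake is limited but real. The PPS is the stated sensitivity population for the primary and all secondary efficacy endpoints. If the rule cannot be run as printed, someone must reinterpret it when the set is determined. The trial is open-label, so that choice would be made with treatment assignments known.

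**Working it through.** **Design figures, to show what is not affected.** Inputs from SAP 9.3: survival 60% against 80%, one-sided Type I error 0.025, power 90%, 2:1 allocation, pooled variance. Pooled survival is (0.6 + 2 × 0.8)/3 = 0.7333. For a fixed design,

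n(control) = [1.960 × √(1.5 × 0.7333 × 0.2667) + 1.2816 × √(0.24 + 0.16/2)]² / 0.2² = (1.0615 + 0.7250)² / 0.04 = 79.8, so 80, or 240 in total.

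The plan's 243 (162 + 81) adds an interim analysis and is close to this; fixed-design power at 162 + 81 is 0.904. Inflation gives 243/0.9 = 270 (180 + 90). None of these figures uses the PPS.

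**Who enters the PPS under each reading.** 'Needed' is what the opening sentence of SAP 6.2 and the list in SAP 7.1.2 imply.

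| Patient | Needed | Both bullets required | Either bullet suffices | Dosing bullet applies to ravulizumab arm only |
|---|---|---|---|---|
| BSC alone, no important deviation | In | **Out** | In | In |
| BSC alone, key eligibility deviation | Out | Out | Out | Out |
| Ravulizumab, no deviation, fully dosed | In | In | In | In |
| Ravulizumab, key eligibility deviation, fully dosed | Out | Out | **In** | Out |
| Ravulizumab, eligible, under-dosed | Out | Out | Out (fails bullet 1 through SAP 7.1.2) | Out |

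The joint reading loses every control patient. The alternative reading keeps them, but admits ravulizumab patients whom the opening sentence excludes. Only the conditional reading gives the needed set, and it is not what is printed.

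**Consequence of the joint reading.** The PPS holds at most 180 ravulizumab and 0 of 90 BSC-alone patients. The Mantel-Haenszel risk difference is Σ wₖ(p₁ₖ − p₀ₖ)/Σ wₖ, with wₖ = n₁ₖn₀ₖ/(n₁ₖ + n₀ₖ) in each intubation stratum. With n₀ₖ = 0 in both strata, every weight is zero and p₀ₖ is undefined, so there is no estimate. The log-rank test has one group. The treatment term in the Cox, ANCOVA and MMRM models is constant and cannot be estimated.

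**After correction.** Up to 180 + 90 patients could qualify. The documents give no PPS retention figure. Assuming equal retention in both arms, fixed-design power for 60% against 80% is:

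| Retention | Ravulizumab + BSC alone | Power |
|---|---|---|
| 100% | 180 + 90 | 0.930 |
| 90% | 162 + 81 | 0.904 |
| 80% | 144 + 72 | 0.869 |
| 70% | 126 + 63 | 0.824 |

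These values only show that the corrected comparison is usable; the plan sets no power target for the PPS.

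**The case against.** The strongest reply is that the intent is plain.

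- The opening sentence of SAP 6.2 has no arm restriction.
- None of the exclusions in SAP 7.1.2 removes a patient for being on BSC alone, and such a patient has no required doses to miss.
- SAP 7.1.3 tabulates the PPS by treatment group.
- SAP 4.1 and 4.2 list the changes from the protocol and from the previous SAP, and a change to the PPS is not among them.
- A set with no controls would be noticed as soon as someone tried to run the comparison.

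All of this stands. A reader might infer from bullet 2 that the sponsor meant a one-arm PPS. The documents do not support that.

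Intent does not, however, supply the rule. The protocol's unrestricted definition does not formally cure the wording, because SAP 4.1 gives the SAP precedence on analyses. SAP 7.1.2 adds exclusions but does not remove an inclusion condition. The Safety Set in SAP 6.3 faces the same asymmetry between arms and handles it by naming the BSC-alone patients explicitly; the PPS lacks that clause.

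It is also fair to say that the PPS is only a sensitivity set. The primary endpoint has other sensitivity analyses on the ITT population, covering missing-data scenarios, a tipping point, time to event, a three-level outcome and covariate adjustment. This limits the consequence and stands in full.

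**Conclusion.** The wording is wrong as printed and should be corrected, but it is a small point. Taken literally, 0 of 90 planned BSC-alone patients qualify and no PPS treatment contrast can be computed. That count rests on reading the bullets as joint conditions, which is the ordinary reading; reading them as alternatives conflicts with the section's own opening sentence.

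Two stronger inferences should be resisted. One is that the trial's main conclusion is at risk. It is not: the ITT population is primary, and the primary test, Type I error, power, stopping boundaries and testing hierarchy do not depend on the PPS. The other is that the plan would hide who is excluded. SAP 7.1.1 already plans a summary of patients in the analysis datasets with reasons for exclusion, so no further reporting request is needed.

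**What to change.** In SAP 6.2, replace the second bullet with a condition that depends on arm and keeps the present ICU limit, for example: *If randomized to ravulizumab + BSC, all required doses were received while the patient was alive and in the treatment period in the ICU. Patients randomized to BSC alone qualify on the first criterion only.* In SAP 7.1.2, state that the dosing item applies to the ravulizumab + BSC arm only. SAP 6.2, its compliance paragraph and SAP 7.1.2 then agree.

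The ICU limit must stay in the bullet. Without it, the bullet would conflict with the compliance paragraph and SAP 7.1.2. It could also exclude ravulizumab patients who died before completing the dosing schedule while keeping BSC-alone patients who died equally early. Removing early deaths from one arm only would bias the PPS survival comparison toward ravulizumab.

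The cost is one sentence and one clause in the SAP, made before the PPS is determined ahead of database lock. Data collection, sample size and the primary analysis do not change, and the dosing condition itself stays as the SAP already has it.
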